## 1. Research background

Gastric cancer is an important type of cancer worldwide, ranking fifth in terms of global cancer incidence and fourth in terms of mortality. In fact, the majority of gastric cancer cases are diagnosed at an advanced stage, with a poor prognosis and limited treatment options. The 5-year survival rate for early-stage gastric cancer is over 90%, while that for advanced gastric cancer is only about 10%.

Therefore, early and precise endoscopic examination is of great significance in reducing the mortality rate of gastric cancer and improving the prognosis of patients. Gastric juice is a digestive fluid that directly contacts the gastric tissue and bypasses the metabolic function of the liver. It contains a large number of shed malignant cells and tumor products, which makes it possible to be an ideal biomarker with satisfactory sensitivity and specificity.

At present, many researchers have begun to focus on gastric juice as a research subject, mainly concentrating on the study of nucleic acid molecules such as miRNA, cirRNA, lncRNA, and microRNA in gastric juice. These molecules are believed to be related to the development and progression of gastric cancer and thus can be used for the diagnosis and prognosis analysis of gastric cancer.

In the existing research, studies on extracellular vesicles in gastric juice are scarce. As an important component of functional molecules in the body, extracellular vesicles play a key role in the development and progression of diseases. By deeply exploring the composition of extracellular vesicles in gastric juice, we can investigate their potential role in the development of gastric cancer, search for possible biomarkers, and thereby provide new clues and basis for the early diagnosis, prognosis assessment, and treatment strategy formulation of gastric cancer.

## 2. Purpose of research

This project aims to study extracellular vesicles in gastric juice under different disease conditions, screen out liquid biopsy markers for the early diagnosis of gastric cancer, and identify biomarkers for disease progression or high-risk populations to achieve early disease prediction, guide endoscopic detailed examination, and reduce missed diagnoses. The research will be conducted at Beijing Friendship Hospital, Capital Medical University. By analyzing the diagnosis and treatment process and gastric juice samples of patients undergoing gastroscopy, the characteristics of extracellular vesicles in gastric cancer patients will be determined, and further guidance for endoscopic detailed examination will be provided. We will conduct the research in accordance with the "Measures for the Ethical Review of Biomedical Research Involving Human Subjects" and the principles of the "Declaration of Helsinki".

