## 3. Research contents

After obtaining informed consent from the patients, all the medical history and treatment records of the patients who underwent gastroscopy since the onset of the disease, as well as gastric fluid samples, including laboratory and imaging data, were collected and recorded. The medical history and treatment records and gastric fluid samples were analyzed and an article was written.

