### **4.2. Subjects**

4.2.1 Study population: patients who underwent gastroscopy and treatment in Beijing Friendship Hospital, Capital Medical University from Dec. 2025 to Dec. 2026.

4.2.2 Research Center: Beijing Friendship Hospital Affiliated to Capital Medical University.

4.2.3 Planned enrollment: 100 patients, in which the ratio of gastric cancer and non-cancer patients was 1:1.

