#### **4.2.4 Inclusion and exclusion criteria**

Inclusion criteria: 1. Patients underwent gastroscopy and treatment at the Endoscopy Center of Beijing Friendship Hospital, Capital Medical University, and received pathological biopsy. 2. Previous gastroscopy suggested the possibility of lesions. 3. No previous history of gastrointestinal cancer.

Exclusion criteria: 1. Patients could not cooperate with the examination or had contraindications to endoscopy. 2. Previous history of gastrointestinal tumors, gastrointestinal surgery, physical and chemical injuries of the gastrointestinal tract. 3. Severe bile reflux. 4. Take simethicone and other defoaming agents before examination. 5. Patients with serious diseases of heart, lung, kidney, brain, blood and other important organs.

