### **4.3 Research process**

1. Patients who met the inclusion criteria were enrolled, and the demographic and medical information of the subjects were collected, including name, gender, age, primary disease, past history, gastroscopic biopsy pathological report, etc.

2. the use of previous studies in gastroscopy drain to collect the clinical routine during the rest of the specimens of gastric juice, extracellular vesicle separation and metabonomics analysis, about 10 to 20 ml/time, according to the result of pathology for specimens of patients with gastric cancer patients and patients with gastric cancer group, the identification of potential biomarkers, diagnosis model is established.

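### The aim is early diagnosis, but the protocol text defines only cancer and non-cancer groups and nowhere names tumour stage or depth

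*Protocol*

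**What the plan says.** - **Aim.** Protocol Section 2 intends "to study extracellular vesicles in gastric juice under different disease conditions", to "screen out liquid biopsy markers for the early diagnosis of gastric cancer", and to "identify biomarkers for disease progression or high-risk populations to achieve early disease prediction". The results are meant to guide detailed endoscopy and reduce missed diagnoses.
- **Groups.** Section 4.2.3 plans "100 patients, in which the ratio of gastric cancer and non-cancer patients was 1:1". Section 4.3 assigns patients by pathology and then plans "the identification of potential biomarkers, diagnosis model is established". Its sentence on grouping reads badly and names gastric cancer twice, so 4.2.3 is the clear source for the two groups.
- **Eligibility.** Section 4.2.4 requires a biopsy, no earlier gastrointestinal cancer, and that "Previous gastroscopy suggested the possibility of lesions". It has no condition on stage or depth.
- **Variables.** Section 4.4 lists demographics, biopsy pathology, physical and chemical properties of gastric juice, and the vesicle analysis. Section 4.3 adds primary disease and past history and leaves its list open. Neither names stage or depth. Section 3 collects full history and treatment records, "including laboratory and imaging data, were collected and recorded".
- **Background.** Section 1 contrasts 5-year survival above 90% in early disease with about 10% in advanced disease, and states that "the majority of gastric cancer cases are diagnosed at an advanced stage".
- **Analysis.** Section 6 provides a t test for two groups and one-way ANOVA for more than two, but no third group is defined in the text.

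**The concern.** The aim concerns early cancer and the defined contrast concerns any cancer. These are different questions. A marker that reflects tumour bulk or extensive shedding could separate the groups well because of the advanced cases and still miss the early ones. The protocol itself treats early and advanced disease as very different in prognosis and describes advanced presentation as the usual case, so pooling the two is not neutral for this aim.

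If only the pooled result is reported, the reader cannot tell whether the marker works in the patients Section 2 is about. The quota adds to this: it fixes the ratio of cancer to non-cancer but no number of early cancers. A later analysis plan can add a subgroup, but it cannot decide who was enrolled.

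A lesser point concerns progression and high-risk populations, which are also named as aims. No progression outcome, follow-up or high-risk group is defined. Prediction can be read as predicting what gastroscopy will find, and the design can address that. Beyond it, the samples support only cross-sectional association.

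**Working it through.** The protocol gives no calculation to reproduce: Section 4.5 states no effect size, SD, rate or power. The case rests on the text; the arithmetic only shows its size.

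**Inputs**
- From the protocol: 100 patients at 1:1, so 100 × 0.5 = 50 cancers and 50 non-cancer patients (4.2.3); significance level 0.05 and t test (Section 6).
- Assumed: two-sided testing, 80% power, 80% observed sensitivity, and 10 to 40 early cancers among the 50. If Section 1's majority-advanced statement held in this sample, fewer than 25 would be early, so 25 is the boundary and 40 is generous to the plan.

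**1. What pooling can hide.** Pooled sensitivity = f × Se(early) + (1 − f) × Se(advanced), where f is the early share. Assume sensitivity of 40% in early and 90% in advanced cancer:
- f = 0.1: 0.04 + 0.81 = 0.85
- f = 0.2: 0.08 + 0.72 = 0.80
- f = 0.5: 0.20 + 0.45 = 0.65

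At f = 0.2 this is 4/10 early plus 36/40 advanced, or 40/50 = 80%. A marker detecting 8/10 early and 32/40 advanced gives the same 40/50. The pooled figure cannot tell the two markers apart.

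**2. Precision in early cancer.** Exact (Clopper-Pearson) 95% limits for x detected of n: lower = Beta quantile 0.025 with parameters (x, n − x + 1); upper = Beta quantile 0.975 with parameters (x + 1, n − x).

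**3. Detectable difference.** Two-sample t test of n early cancers against 50 non-cancer patients. Solve for the d that gives power 0.80 under the noncentral t distribution with n + 48 degrees of freedom and noncentrality d / √(1/n + 1/50).

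| Cancers in the contrast | Detected at 80% | Exact 95% CI | Detectable difference (SD) |
|---|---|---|---|
| 10 early | 8/10 | 0.444-0.975 | 0.99 |
| 20 early | 16/20 | 0.563-0.943 | 0.75 |
| 25 early | 20/25 | 0.593-0.932 | 0.70 |
| 40 early | 32/40 | 0.644-0.909 | 0.60 |
| 50, pooled | 40/50 | 0.663-0.900 | 0.57 |

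*Cross-check.* The normal approximation d = (1.960 + 0.842) × √(1/50 + 1/n) gives 2.802 × √0.12 = 0.97 for n = 10, 2.802 × √0.06 = 0.69 for n = 25, and 2.802 × √0.04 = 0.56 for n = 50. These lie slightly below the t-test values, as expected.

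*Fewer early cases.* With only 5, 4/5 detected gives 0.284-0.995, and the detectable difference is about 1.31 SD by the normal approximation.

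*Missing stage.* If stage is unknown for one in five of 25 early cancers, 25 × 0.8 = 20 remain, and the 20-case row applies.

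**The case against.** The strongest objection is that finer groups may be defined where they cannot be read. In the copy reviewed, the Technical route section has no text and a figure is not reproduced. Section 2 speaks of differing disease conditions, and Section 6 allows for more than two groups. A finer grouping in the missing material cannot be excluded, so the conclusion is limited to the readable text. The two phrases alone define no group.

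Second, stage may be available. Section 3 collects full records with imaging, and the list in 4.3 is open. This stands: the finding is that stage is not named or used, not that it cannot be obtained. It also makes the remedy cheap.

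Third, separate reporting and the handling of unknown stage are often left to the SAP, which is not shown. That is fair for the analysis details. The aim, the target groups, eligibility and the main variables are protocol content.

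Fourth, the majority-advanced statement is general background. The stage mix at this endoscopy centre could differ in either direction, which is why the counts above are assumptions shown over a range.

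Finally, the study is exploratory: Section 4.5 calls it descriptive, and screening for markers is discovery work. Candidate markers of prevalent gastric cancer remain a valid output. But the protocol also plans a diagnostic model and intends to guide endoscopy, which goes beyond description.

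**Conclusion.** The concern holds. As the text stands, the study compares gastric cancer with non-cancer, and a pooled result from that comparison cannot support a conclusion about early diagnosis. No figure in the protocol is wrong; the mismatch is between the aim and the defined contrast.

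Its size depends on the unknown number of early cases. For 10 to 25 early cancers, the detectable difference is about 1.2 to 1.7 times the pooled one (0.70/0.57 and 0.99/0.57). The interval around 80% sensitivity is about 34 to 53 percentage points wide, against about 24 pooled. Beyond the counts, this assumes 80% observed sensitivity, 80% power and two-sided testing. Confidence is medium because part of the protocol's content could not be read. The change should be made, but the gap does not invalidate the study as a search for candidate markers.

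**What to change.** - **Section 4.4:** name tumour depth or stage as a variable, state that it comes from the records and imaging collected under Section 3, and say how patients with unknown stage are handled.
- **Reporting:** give early cancer versus non-cancer separately from advanced cancer versus non-cancer, each with confidence intervals.
- **Conclusions:** base any early-diagnosis statement on the early-cancer contrast. If early cases are too few, limit the conclusion to candidate markers of prevalent gastric cancer.
- **Section 2:** limit the progression and prediction aims to cross-sectional association with pathology, unless an outcome or a high-risk group is defined.

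The cost is wording in Sections 2 and 4.4 plus record extraction, with no extra patients or procedures. Stage may be incomplete, and finding it may take more than one field per patient. The change creates no early cases, so the early-cancer interval may be wide and the final claim narrower than Section 2 now suggests.

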## 3. Research contents

After obtaining informed consent from the patients, all the medical history and treatment records of the patients who underwent gastroscopy since the onset of the disease, as well as gastric fluid samples, including laboratory and imaging data, were collected and recorded. The medical history and treatment records and gastric fluid samples were analyzed and an article was written.

## **4. Study protocol**

### **4.1. Study design**

Observational study (retrospective)

### **4.2. Subjects**

4.2.1 Study population: patients who underwent gastroscopy and treatment in Beijing Friendship Hospital, Capital Medical University from Dec. 2025 to Dec. 2026.

4.2.2 Research Center: Beijing Friendship Hospital Affiliated to Capital Medical University.

4.2.3 Planned enrollment: 100 patients, in which the ratio of gastric cancer and non-cancer patients was 1:1.

#### **4.2.4 Inclusion and exclusion criteria**

Inclusion criteria: 1. Patients underwent gastroscopy and treatment at the Endoscopy Center of Beijing Friendship Hospital, Capital Medical University, and received pathological biopsy. 2. Previous gastroscopy suggested the possibility of lesions. 3. No previous history of gastrointestinal cancer.

Exclusion criteria: 1. Patients could not cooperate with the examination or had contraindications to endoscopy. 2. Previous history of gastrointestinal tumors, gastrointestinal surgery, physical and chemical injuries of the gastrointestinal tract. 3. Severe bile reflux. 4. Take simethicone and other defoaming agents before examination. 5. Patients with serious diseases of heart, lung, kidney, brain, blood and other important organs.

### **4.3 Research process**

1. Patients who met the inclusion criteria were enrolled, and the demographic and medical information of the subjects were collected, including name, gender, age, primary disease, past history, gastroscopic biopsy pathological report, etc.

2. the use of previous studies in gastroscopy drain to collect the clinical routine during the rest of the specimens of gastric juice, extracellular vesicle separation and metabonomics analysis, about 10 to 20 ml/time, according to the result of pathology for specimens of patients with gastric cancer patients and patients with gastric cancer group, the identification of potential biomarkers, diagnosis model is established.

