#### **4.4 Observation target**

- (1) Demographic data and clinical information: name, age, gender;
- (2) Pathological results of endoscopic tissue biopsy;
- (3) Physical and chemical properties of gastric juice (pH value, absorbance, etc.);
- (4) Diagnostic analysis of extracellular vesicles in gastric juice.

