#### **4.5 Determination of Sample Size**

This study is an observational and descriptive one, with no specific sample size requirement. However, based on current domestic and international literature reports, approximately 100 cases are expected to be needed. Meanwhile, adjustments will be made as appropriate considering the situation of patient loss to follow-up and incomplete sample information in our center that cannot be used.

[figure not shown]

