### **5. Technical route**

## **6. Statistical method**

Statistical software SPSS19.0 was used to analyze the data of this cohort study, and P value < 0.05 was considered statistically significant. For quantitative data, if the data were in accordance with the normal distribution, the mean  $\pm$  standard deviation was used to describe the data. The t test was used for comparison between two groups, and the one-way analysis of variance was used for comparison between multiple groups. If the data did not meet the normal distribution, "median" was used to describe the data, and the differences were compared using the Mann-Whitney rank sum test. For qualitative data, "rate (95%CI)" was used to describe, chi-square test was used to compare the differences between groups, and Logistic regression was used for cross-sectional multivariate analysis of risk factors.

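### The methods stated in Section 6 do not estimate how the diagnosis model of Section 4.3 performs in new patients; used alone on the same patients, they would overstate its accuracy

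*Protocol*

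**What the plan says.** Protocol Section 4.3 describes "extracellular vesicle separation and metabonomics analysis" on leftover gastric juice, grouping of specimens by pathology, and then "the identification of potential biomarkers, diagnosis model is established". Section 4.4 lists "Diagnostic analysis of extracellular vesicles in gastric juice" among the observation targets. Section 2 gives the purpose as finding markers for earlier detection of gastric cancer and for guiding endoscopy, which means use in patients outside the study sample.

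Section 4.2.3 plans "100 patients, in which the ratio of gastric cancer and non-cancer patients was 1:1", and Section 4.2.2 names one center. Section 4.5 says that "approximately 100 cases are expected to be needed", with room for adjustment.

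Section 6 opens with "Statistical software SPSS19.0 was used to analyze the data of this cohort study" and sets the threshold "P value < 0.05 was considered statistically significant". It then names the t test, analysis of variance, the Mann-Whitney test, the chi-square test and rates with 95% CI. On regression it says "Logistic regression was used for cross-sectional multivariate analysis of risk factors".

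**The concern.** Sections 4.3 and 4.4 promise a diagnostic model, while Section 6 describes group comparisons and a risk-factor regression. The statistical section is specific enough to name software, significance level and tests, but no method in it answers the question that a diagnostic model raises: how well does it classify patients who did not help to build it?

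If the Section 6 methods were all that was used, any accuracy figure would come from the patients who supplied the markers and the model coefficients. Selection favours features that separate these 100 patients partly by chance, and the fit then adapts to the same chance pattern. AUC, sensitivity and specificity would be too high on average. Because the purpose is early diagnosis, that accuracy is what readers will look for, and a set of features with no diagnostic value could look promising.

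**Working it through.** **The plan's own figure.** 100 patients at 1:1 gives 100 / 2 = 50 with cancer and 50 without. The 100 itself cannot be reproduced or refuted, because Section 4.5 gives no accuracy target, effect size, power or precision.

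**Stated methods against the task.**
- Two-group and multi-group tests compare distributions. They give no accuracy for a model.
- Rates with 95% CI could describe sensitivity or specificity, but only in the patients at hand.
- Logistic regression can produce a score. Assessed on the patients used to fit it, the score gives apparent accuracy only.

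**Simulation.** From the protocol: 50 v 50. Assumed, because the protocol does not give them:
- m candidate features, independent and normal
- the number that truly differ between groups, and by how much (in SD)
- selection by t test, keeping either those with P < 0.05 or the top k
- a logistic model on the features kept

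The score's AUC is (R1 − n1(n1+1)/2) / (n1·n0), where R1 is the rank sum of scores in the cancer group and n1, n0 are the group sizes. It is computed in the same 100 patients and in simulated new patients. The gap is AUC(same) − AUC(new). The last column is 10-fold cross-validation with selection repeated inside each fold. Entries are means over 150 datasets per setting; other runs with 200 to 400 datasets agreed to within about 0.01.

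| Candidates | Real markers | Kept | Same | New | Gap | Cross-validated |
|---|---|---|---|---|---|---|
| 20 | none | top 5 | 0.70 | 0.50 | 0.20 | 0.50 |
| 100 | none | top 5 | 0.78 | 0.50 | 0.28 | 0.49 |
| 1000 | none | top 5 | 0.85 | 0.50 | 0.35 | 0.50 |
| 5 | 3 at 0.5 SD | all | 0.76 | 0.71 | 0.05 | 0.70 |
| 20 | 5 at 0.5 SD | P < 0.05 | 0.81 | 0.72 | 0.09 | 0.71 |
| 100 | 10 at 0.5 SD | top 5 | 0.87 | 0.74 | 0.13 | 0.73 |
| 1000 | 10 at 0.5 SD | top 5 | 0.88 | 0.67 | 0.21 | 0.65 |

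In the fifth row's setting, sensitivity/specificity at the Youden cut-off was 0.78/0.73 in the same patients and 0.68/0.63 in new ones.

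**Stronger markers.** Same design with markers of 1.0 SD, 300 datasets per setting:

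| Candidates | Real markers | Kept | Same | New | Gap |
|---|---|---|---|---|---|
| 20 | 2 | top 2 | 0.844 | 0.836 | 0.01 |
| 20 | 5 | P < 0.05 | 0.955 | 0.929 | 0.03 |
| 100 | 5 | top 5 | 0.952 | 0.931 | 0.02 |
| 100 | 10 | P < 0.05 | 0.999 | 0.958 | 0.04 |
| 1000 | 10 | top 5 | 0.973 | 0.936 | 0.04 |

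**No selection, one prespecified marker of 0.5 SD.** 0.63 v 0.64, so no gap.

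**Reading.** On average the gap is upward in every setting with selection. It is large when signal is weak or absent, and small when markers are strong. Cross-validation with selection inside the folds comes within about 0.02 of the new-patient AUC throughout the first table.

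**The case against.** The best counter-argument is that this is missing detail rather than an error. How a model is validated is often left to an SAP, which is not at hand, and one figure was not available for this check. Section 5, the technical route, is a bare heading in the text seen, and such a diagram could well show discovery and validation stages. The study also calls itself descriptive and speaks only of potential markers.

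Much of this stands, and it rules out three stronger readings that a reader might infer:
- **That the study has no validation, or will report same-patient accuracy.** No sentence says so. AUC, sensitivity and specificity are not mentioned in the visible text at all.
- **That Section 6 selects markers at P < 0.05 and builds the model by logistic regression.** It calls P < 0.05 significant without making it a selection rule, and it assigns logistic regression to risk factors. Both links are assumptions of the simulation.
- **That the number of candidates alone fixes the bias.** The large gaps in the first table hold for absent markers or markers of 0.5 SD. At 1.0 SD the gap almost closes, even with 1000 candidates.

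The mismatch inside the protocol remains. Section 6 presents itself as the analysis of the study data, Section 4.3 commits to choosing markers and establishing a model, and the stated methods do not assess that model. Following Section 6 as written would leave only same-patient accuracy.

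**Conclusion.** The concern holds in conditional form. The methods that Section 6 states do not estimate the diagnosis model's accuracy in new patients. If markers are selected and the model is fitted and assessed in the same 50 v 50 patients with these methods alone, accuracy is biased upward.

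The direction is firm under that reading; the size is not. It rests on assumed numbers of candidates, selection rules and signal strengths, with independent normal features. Across the settings tabulated, the AUC gap runs from 0.20 to 0.35 with no real marker, from 0.05 to 0.21 with markers of 0.5 SD, and about 0.01 to 0.04 with markers of 1.0 SD. The 50 v 50 is itself a plan that Section 4.5 allows to change.

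**What to change.** Add a short paragraph to Section 6 stating that:
- AUC, sensitivity and specificity of the diagnosis model are estimated by internal validation in which every data-driven step (marker selection, scaling, tuning, choice of cut-off) is repeated inside each training set, for example by repeated stratified 10-fold cross-validation;
- accuracy in the patients used for fitting, if shown, is labelled as apparent and is not the headline result;
- the model is reported as exploratory.

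If a validation split is already planned, state it there instead. The type of model can stay open. The method for the 95% CI can be left to the SAP, provided it accounts for the marker selection.

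The change needs no extra patients or samples. Its costs are a less favourable accuracy figure, some analysis outside SPSS 19.0, slight pessimism of cross-validation (up to about 0.02 in AUC), and an imprecise estimate at 50 v 50: the SD of one study's cross-validated AUC is about 0.07 to 0.10 in the simulations. The rule is most credible if fixed before the data are analyzed.
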